9.6.2 Statistical Methods for Safety Analyses

Safety and tolerability will be assessed by clinical review of all relevant parameters.

The analysis of safety will be performed for each of the V181 Potency Level groups (V181 High Potency Level, V181 Mid Potency Level, V181 Low Potency Level) versus placebo following a tiered approach (Table 5). The tiers differ with respect to the analyses that will be performed. Adverse events (specific terms as well as SOC terms) are either pre-specified as “Tier1” endpoints or will be classified as belonging to “Tier 2” or “Tier 3” based on the number of events observed. A separate safety analysis will be performed with comparisons between the V181 High Potency Level vs the V181 Mid Potency Level as well as the V181 Low Potency Level vs the V181 Mid Potency Level. This analysis will include comparisons with the following tables: overall AE summary, solicited injection site AEs, solicited systemic AEs, and distribution of maximum temperatures.

Tier 1 Events

Safety parameters or adverse events of special interest that are identified *a priori* constitute “Tier 1” safety endpoints that will be subject to inferential testing for statistical significance. There are no Tier 1 events for this protocol as there is no formal safety hypothesis.

Tier 2 Events

Tier 2 parameters will be assessed via point estimates with 95% CIs provided for differences in the proportion of participants with events (Miettinen and Nurminen [M&N] method [1985] [Miettinen, O. and Nurminen, M. 1985]).

Membership in Tier 2 requires that at least 4 participants in any treatment group exhibit the event. The threshold of at least 4 events was chosen because the 95% confidence interval for the between-group difference in percent incidence will always include zero when treatment groups of equal size each have less than 4 events and thus would add little to the interpretation of potentially meaningful differences. Because many 95% CIs for Tier 2 events may be provided without adjustment for multiplicity, the CIs should be regarded as a helpful descriptive measure to be used in review, not a formal method for assessing the statistical significance of the between-group differences in AEs.

In addition to individual events that occur in 4 or more participants in any treatment group, the broad AE categories consisting of the proportion of participants with any AE, a vaccine-related AE, an MAAE, a vaccine-related MAAE, an SAE, a vaccine-related SAE, discontinuation due to an AE, and death will be considered Tier 2 endpoints. Solicited injection-site AEs (pain, erythema, and swelling) from Day 1 through Day 5 postvaccination, solicited systemic AEs (rash, headache, fatigue [tiredness], myalgia [muscle pain], and arthralgia [joint pain]) from Day 1 through Day 28 postvaccination, and vaccine-related SAEs from Day 1 through Day 28 postvaccination will also be considered a Tier 2 endpoint.

Tier 3 Events

Safety endpoints that are not Tier 1 or 2 events are considered Tier 3 events. Only point estimates by treatment group are provided for Tier 3 safety parameters.

Table 5 Analysis Strategy for Safety Parameters

Safety Tier	Safety Endpoint ^a	95% CI for Treatment Comparison	Descriptive Statistics
Tier 2	Any AE ^a	X	X
	Any vaccine-related AE ^a	X	X
	Any MAAE ^a	X	X
	Any vaccine-related MAAE ^a	X	X
	Any SAE ^a	X	X
	Any vaccine-related SAE ^a	X	X
	Discontinuation due to AE ^a	X	X
	Death ^a	X	X
	Solicited injection-site AEs: pain, erythema, and swelling	X	X
	Solicited systemic AEs: rash, headache, fatigue (tiredness), myalgia (muscle pain), and arthralgia (joint pain)	X	X
	Elevated temperature ($\geq 100.4^{\circ}\text{F}$ [38.0°C] oral equivalent)	X	X
	Specific AEs by SOC and PT ^b (incidence ≥ 4 participants in one of the vaccination groups)	X	X
Tier 3	Specific AEs by SOCs and PT ^b (incidence < 4 participants in all of the vaccination groups)		X

AE = adverse event; CI = confidence interval; MAAE – medically attended adverse event; PT = preferred term; SAE = serious adverse event; SOC=system organ class; X = results will be provided
 
^a These endpoints are broad AE categories. For example, descriptive statistics for the safety endpoint of “Any AE” will provide the number and percentage of participants with at least one AE.
 
^b Includes only those endpoints not already pre-specified as Tier 2 endpoints.
			

9.6.3 Summaries of Baseline Characteristics, Demographics, and Other Analyses

The comparability of the vaccination groups for each relevant characteristic will be assessed by the use of tables and/or graphs. No statistical hypothesis tests will be performed on these characteristics. The number and percentage of participants screened and randomized, the primary reasons for screening failure, and the primary reason for discontinuation will be displayed. Demographic variables (eg, age), baseline characteristics, primary and secondary

diagnoses, and prior and concomitant therapies will be summarized by vaccination group either by descriptive statistics or categorical tables.

9.7 Interim Analyses

No interim analyses are planned for this study. Participant safety will be monitored by an eDMC that will perform periodic reviews of safety data throughout the study (Appendix 1). An unblinded statistician and statistical programmer not directly involved in the conduct of the study will be responsible for providing unblinded report deliverables to the eDMC. Details will be provided in the eDMC charter.

9.8 Multiplicity

No multiplicity adjustment is needed for this study as success is required on all 4 dengue serotypes.

9.9 Sample Size and Power Calculations

9.9.1 Sample Size and Power for Immunogenicity Analyses

This study will randomize participants in a 2:4:4:1 ratio into the 4 vaccination groups (V181 High Potency Level Group, V181 Mid Potency Level Group, V181 Low Potency Level Group, and Placebo). The overall sample size will be approximately 1265 with 230 participants in the High Potency Level Group, 460 participants in each of the Mid and Low Potency Level Groups, and 115 participants in the placebo group. The study has an overall power of >95% to establish that the V181 Low Potency Level is non-inferior to the V181 Mid Potency Level for all four serotypes at an overall one-sided, 2.5% alpha-level. The power and sample size are based on the following assumptions: 1) an approximately 15% non-evaluable rate, 2) the non-inferiority margin of 0.67, 3) the true GMT ratio is assumed to be 1, and 4) the standard deviation of the natural-log titers is estimated to be 1.25 for each dengue serotype based on previous clinical and assay data. Given these assumptions, using the most conservative standard deviation, the lowest estimated GMT ratio that would meet a lower bound criterion of 0.67 is approximately 0.78.

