9.6.1 Statistical Methods for Immunogenicity Analyses

The primary hypothesis of non-inferiority of GMTs for each dengue serotype (DENV1, DENV2, DENV3, and DENV4) will be addressed by 4 one-sided tests of non-inferiority (one corresponding to each dengue serotype) conducted at $\alpha=0.025$ level (1-sided). For each dengue serotype, the hypotheses to be tested are:

$$H_0: \text{GMT}_x/\text{GMT}_y \leq 0.67$$

Versus

$$H_1: \text{GMT}_x/\text{GMT}_y > 0.67$$

where GMT_x represents the GMT at 28 days postvaccination in the V181 Low Potency Level group and GMT_y represents the GMT at Day 28 postvaccination in the V181 Mid Potency Level group. Estimation of the GMT ratios and computation of the corresponding 95% CIs will be calculated using t-distribution with the variance estimate from a linear model utilizing the log-transformed antibody titers as the response and a single term for vaccination group. The point estimates will be calculated by exponentiating the estimates of the mean of the natural log values and the CIs will be derived by exponentiating the CIs of the mean of the natural log values based on the model. The statistical criterion for non-inferiority requires that the lower bound of two-sided 95% confidence interval of GMT ratio (V181 Low Potency Level vs. V181 Mid Potency Level) being greater than 0.67.

CCI

CCI

[Clopper, C. J. 1934].

Table 4 Analysis Strategy for Immunogenicity Variables

Endpoint/Variable (Description, Time Point)	Primary vs. Supportive Approach ^a	Statistical Method ^b	Analysis Population	Missing Data Approach
Primary Endpoint				
Dengue virus-neutralizing antibody GMTs for each of the 4 dengue serotypes at Day 28 postvaccination as measured by VRNT	P S	t-distribution with the variance estimate from a linear model ^b (estimate, 95% CI, p-value)	PP FAS	Missing data will not be imputed

CI = confidence interval; FAS = Full Analysis Set; GMT = Geometric Mean Titer; PP = Per-Protocol

^a P=Primary approach; S=Supportive approach.

^b Estimation of the dengue virus-neutralizing antibody GMTs and computation of the corresponding 95% CIs will be calculated using t-distribution with the variance estimate from a linear model utilizing the log-transformed antibody titers as the response and a single term for vaccination group.

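### The lowest passing GMT ratio in Section 9.9.1 should be about 0.80, not 0.78: under the plan's own assumptions an observed 0.78 or 0.79 fails non-inferiority

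*Combined protocol and SAP*

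**What the plan says.** Section 9.9.1 (Sample Size and Power for Immunogenicity Analyses) plans for "460 participants in each of the Mid and Low Potency Level Groups". It assumes "an approximately 15% non-evaluable rate", "the non-inferiority margin of 0.67", and that "the true GMT ratio is assumed to be 1". On variability it says that "the standard deviation of the natural-log titers is estimated to be 1.25 for each dengue serotype". From these assumptions, and saying that it uses the most cautious SD, it concludes that "the lowest estimated GMT ratio that would meet a lower bound criterion of 0.67 is approximately 0.78". It also claims overall power above 95% for all four serotypes.

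Sections 3 and 9.6.1 set the decision rule. For each serotype the lower limit of the two-sided 95% confidence interval for the Low/Mid GMT ratio must exceed 0.67. The interval uses a t quantile and the variance from a linear model on natural-log titers with vaccination group as the only term. Section 9.8 requires success on all four serotypes.

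**The concern.** The threshold is fully determined by four quantities that the plan states: margin, SD, evaluable number per arm and confidence level. It can therefore be checked directly, and the printed value looks too low.

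This figure is the only place where the plan translates the non-inferiority criterion into an observed loss of titer that the trial could show and still succeed. Sections 4.1, 4.2 and 4.3 say that the study supports the potency release specifications, and Section 4.3 makes the lower-versus-target comparison the key criterion. A reader who relies on 0.78 would expect a serotype observed at 0.78 or 0.79 to meet the criterion. Under the plan's assumptions it would not, and one failing serotype fails the primary hypothesis. The error is in the favourable direction.

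**Working it through.** **Inputs**

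- Randomized per arm, Low and Mid: 460 (Section 9.9.1)
- Non-evaluable: 15% (Section 9.9.1), so n = 0.85 × 460 = 391 evaluable per arm
- SD of natural-log titer: 1.25 for each serotype (Section 9.9.1)
- Margin: 0.67 (Sections 3, 9.6.1 and 9.9.1)
- True ratio for power: 1 (Section 9.9.1)
- Rule: two-sided 95% CI, equivalent to one-sided 0.025 per serotype (Section 9.6.1)

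**Step 1. Reproduce the plan's power, to confirm that the inputs are read correctly.**

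SE = SD × √(2/n) = 1.25 × √(2/391) = 0.0894.

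Power per serotype = Φ(−ln 0.67 / SE − 1.960) = Φ(0.4005/0.0894 − 1.960) = Φ(2.52) = 0.994.

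Four serotypes, if independent: 0.9941⁴ = 0.977 (0.976 with the t distribution). The claim of more than 95% reproduces.

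**Step 2. Compute the lowest passing ratio from the same inputs.**

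Threshold = 0.67 × exp(c × SE).

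- With t on 780 df, c = 1.963: 0.67 × exp(1.963 × 0.0894) = 0.67 × exp(0.1755) = 0.7985
- With the normal quantile 1.960: 0.798
- With t on the pooled degrees of freedom of all four groups: 0.798

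The plan's 0.78 does not reproduce.

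**Step 3. Lower 95% limits at candidate observed ratios (SD 1.25, t quantile).**

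| Observed ratio | 391 per arm | 460 per arm (no loss) |
|---|---|---|
| 0.78 | 0.654, fail | 0.6635, fail |
| 0.79 | 0.663, fail | 0.672, pass |
| 0.80 | 0.671, pass | 0.6805, pass |

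**Step 4. See whether another reading gives 0.78.**

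| Variant | Threshold |
|---|---|
| No loss, n = 460 | 0.788 |
| 5% loss | 0.791 |
| 10% loss | 0.794 |
| Margin 2/3, n = 391 | 0.794 |
| Margin 2/3, n = 460 | 0.784 |
| 90% CI (quantile 1.645), n = 391 | 0.776 |

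Only the last two variants round to 0.78. The first of them contradicts both the stated 0.67 and the stated 15% loss; the second contradicts the 95% CI rule.

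Under the stated rule, 0.78 needs an SD of about 1.08 at 391 per arm, or about 520 evaluable per arm at SD 1.25. Even 0.785, the edge of rounding to 0.78, needs about 479 evaluable per arm, and only 460 are randomized.

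**The case against.** The arithmetic is not in dispute; the case on the other side concerns consequence and remedy.

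First, 0.78 is an illustration. It enters no test, population or sample size, and success will be judged on the confidence interval computed from the trial's own variance. Nobody could declare non-inferiority from this sentence. That stands, and it limits the consequence to planning and reporting. The documents also do not say that a pre-trial threshold ratio will set the specification; they say that the Day 28 results will support it.

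Second, whether 0.78 or 0.79 fails in practice depends on the realised SD and evaluable number. At 391 per arm, 0.79 would pass with a realised SD of about 1.17 or lower, and 0.78 with one below about 1.08. At SD 1.25, 0.79 would pass if all 460 were evaluable. This is correct, but the plan presents its figure as following from its assumptions, and under those assumptions both ratios fail. At SD 1.25, failure at 0.78 does not depend on the 15% loss.

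Third, the mismatch alone does not prove that 0.78 is the wrong item; one of the inputs might be. The power claim cannot settle this, because an SD of 1.08 at 391 per arm would also give more than 95% (about 99.7% for four serotypes). The reference to a most cautious SD hints that others were considered, but 1.25 is the only one printed and a larger one would raise the threshold further. This point bears on how the correction is worded.

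**Conclusion.** The concern holds. Under the assumptions printed in Section 9.9.1 and the rule in Section 9.6.1, the lowest passing observed GMT ratio is 0.7985, about 0.80, not 0.78. The tolerated observed loss is about 20% (1 − 0.80) rather than 22% (1 − 0.78). The word approximately in the plan does not cover the gap, since 0.78 fails even with no loss of participants.

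The result assumes 391 evaluable per arm, SD 1.25 in both arms and a two-sided 95% interval; the choice of t or normal quantile does not matter at two decimals. The error is confined to one descriptive figure. Sample size, power, margin and the primary test stand as they are. How 0.78 was obtained is not documented.

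**What to change.** In Section 9.9.1, replace the value 0.78 with approximately 0.80, and add in brackets the inputs behind it: 391 evaluable per arm and SD 1.25. If the sponsor finds that 0.78 came from a different SD, evaluable number or confidence level, the listed assumptions should be corrected to match, because the sentence as it stands misstates its own basis.

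The cost is one number and a short parenthesis. The summary in Section 9.1 does not repeat the figure, so nothing else has to change. The stated tolerance becomes slightly less favourable.

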9.9.2 Sample Size and Power for Safety Analyses

The probability of observing at least 1 vaccine-related SAE in this study depends on the number of participants vaccinated and the underlying percentage of participants with a vaccine-related SAE in the study population. If the underlying incidence of a vaccine-related SAE is 0.30% (1 of every 333 participants receiving the vaccine), there is a 50% chance of observing at least 1 vaccine-related SAE among 230 participants in the V181 High Potency Level vaccination group. If the incidence rate is 1 of every 144 recipients (0.69%), there is an 80% chance of observing at least 1 vaccine-related SAE. If no vaccine-related SAEs are observed among the 230 participants in the V181 High Potency Level vaccination group, this study will provide 97.5% confidence that the underlying percentage of participants with vaccine-related SAE is <1.6% in the V181 High Potency Level vaccination group.

Table 6 summarizes the percentage point differences between the 2 vaccination groups that could be detected with 80% probability for a variety of hypothetical underlying incidences of an AE. These calculations assume 230 participants in the V181 High Potency Level group and 115 participants in the Placebo group, and are based on a 2-sided 5% alpha level. The calculations are based on an asymptotic method proposed by Farrington and Manning[Farrington, C. P. and Manning, G. 1990]; no multiplicity adjustments were made.

Table 6 Differences in Incidence of Adverse Event Rates Between the 2 Vaccination Groups That Can be Detected With an ~80% Probability (Assuming a 2-Sided 5% Alpha Level With 230 Participants in the V181 High Potency Level Group and 115 Participants in the Placebo Group)

Incidence of an Adverse Event		Risk Difference
V181 High Potency Level Group (%)	Placebo (%)	Percentage Points
5.7	0.1	5.6
9.8	2.0	7.8
14.7	5.0	9.7
21.9	10.0	11.9
28.3	15.0	13.3
34.3	20.0	14.3
45.5	30.0	15.5

Incidences presented here are hypothetical and do not represent actual adverse experiences in either group. Based on an asymptotic method proposed by Farrington and Manning (1990) [Farrington, C. P. 1990]

If the underlying incidence of a vaccine-related SAE is 0.15% (1 of every 665 participants receiving the vaccine), there is a 50% chance of observing at least 1 vaccine-related SAE among 460 participants in the V181 Mid Potency Level and V181 Low Potency Level Groups. If the incidence rate is 1 of every 287 recipients (0.35%), there is an 80% chance of observing at least 1 vaccine-related SAE. If no vaccine-related SAEs are observed among the 460 participants in each of the V181 Mid Potency Level and V181 Low Potency Level Groups, this study will provide 97.5% confidence that the underlying percentage of participants with vaccine-related SAE is <0.9% in each of the V181 Mid Potency Level and V181 Low Potency Level Groups.

Table 7 summarizes the percentage point differences between the 2 vaccination groups that could be detected with 80% probability for a variety of hypothetical underlying incidences of an AE. These calculations assume 460 participants in the V181 Mid Potency Level or V181 Low Potency Level Group and 115 participants in the Placebo group, and are based on a 2-sided 5% alpha level. The calculations are based on an asymptotic method proposed by Farrington and Manning (1990) [Farrington, C. P. and Manning, G. 1990]; no multiplicity adjustments were made.

Table 7 Differences in Incidence of Adverse Event Rates Between the 2 Vaccination Groups That Can be Detected With an ~80% Probability (Assuming a 2-Sided 5% Alpha Level With 460 Participants in the V181 Mid Potency Level or V181 Low Potency Level Group and 115 Participants in the Placebo Group)

Incidence of an Adverse Event		Risk Difference
V181 Mid/Low Potency Level Group (%)	Placebo (%)	Percentage Points
5.0	0.1	4.9
9.0	2.0	7.0
13.8	5.0	8.8
20.8	10.0	10.8
27.1	15.0	12.1
33.0	20.0	13.0
44.2	30.0	14.2

Incidences presented here are hypothetical and do not represent actual adverse experiences in either group. Based on an asymptotic method proposed by Farrington and Manning (1990) [Farrington, C. P. 1990]

9.10 Subgroup Analyses

The subgroup analyses will be comprised of descriptive summary statistics for immunogenicity by gender and age. Further details of subgroup analyses will be documented in the ssAP.

9.11 Compliance (Medication Adherence)

Given that participants will receive only a single dose of 1 of 3 V181 potency levels or placebo, compliance will not be calculated. The number and proportion of randomized participants receiving each study vaccination will be summarized (see Section 9.12).

9.12 Extent of Exposure

The extent of exposure will be summarized by the number and proportion of randomized participants administered each of the 3 V181 potency levels and randomized participants administered placebo.

10 SUPPORTING DOCUMENTATION AND OPERATIONAL CONSIDERATIONS

10.1 Appendix 1: Regulatory, Ethical, and Study Oversight Considerations

10.1.1 Code of Conduct for Clinical Trials

Merck Sharp & Dohme LLC, Rahway, NJ, USA (MSD)

Code of Conduct for Interventional Clinical Trials

I. Introduction

A. Purpose

MSD, through its subsidiaries, conducts clinical trials worldwide to evaluate the safety and effectiveness of our products. As such, we are committed to designing, implementing, conducting, analyzing, and reporting these trials in compliance with the highest ethical and scientific standards. Protection of participants in clinical trials is the overriding concern in the design and conduct of clinical trials. In all cases, MSD clinical trials will be conducted in compliance with local and/or national regulations (including all applicable data protection laws and regulations), and International Council for Harmonisation Good Clinical Practice (ICH-GCP), and also in accordance with the ethical principles that have their origin in the Declaration of Helsinki.

B. Scope

Highest ethical and scientific standards shall be endorsed for all clinical interventional investigations sponsored by MSD irrespective of the party (parties) employed for their execution (e.g., contract research organizations, collaborative research efforts). This Code is not intended to apply to trials that are observational in nature, or which are retrospective. Further, this Code does not apply to investigator-initiated trials, which are not under the full control of MSD.

II. Scientific Issues

A. Trial Conduct

1. Trial Design

Except for pilot or estimation trials, clinical trial protocols will be hypothesis-driven to assess safety, efficacy and/or pharmacokinetic or pharmacodynamic indices of MSD or comparator products. Alternatively, MSD may conduct outcomes research trials, trials to assess or validate various endpoint measures, or trials to determine patient preferences, etc.

The design (i.e., participant population, duration, statistical power) must be adequate to address the specific purpose of the trial and shall respect the data protection rights of all participants, trial site staff and, where applicable, third parties. Participants must meet protocol entry criteria to be enrolled in the trial.

2. Site Selection

MSD selects investigative sites based on medical expertise, access to appropriate participants, adequacy of facilities and staff, previous performance in clinical trials, as well as budgetary considerations. Before trial initiation, sites are evaluated by MSD personnel (or individuals acting on behalf of MSD) to assess the ability to successfully conduct the trial.

3. Site Monitoring/Scientific Integrity

Investigative trial sites are monitored to assess compliance with the trial protocol and Good Clinical Practice (GCP). MSD reviews clinical data for accuracy, completeness, and consistency. Data are verified versus source documentation according to standard operating procedures. Per MSD policies and procedures, if potential fraud, scientific/research misconduct, privacy incidents/breaches or Clinical Trial-related Significant Quality Issues are reported, such matters are investigated. When necessary, appropriate corrective and/or preventative actions are defined and regulatory authorities and/or ethics review committees are notified.

B. Publication and Authorship

Regardless of trial outcome, MSD commits to publish the primary and secondary results of its registered trials of marketed products in which treatment is assigned, according to the pre-specified plans for data analysis. To the extent scientifically appropriate, MSD seeks to publish the results of other analyses it conducts that are important to patients, physicians, and payers. Some early phase or pilot trials are intended to be hypothesis-generating rather than hypothesis testing; in such cases, publication of results may not be appropriate since the trial may be underpowered and the analyses complicated by statistical issues such as multiplicity.

MSD's policy on authorship is consistent with the recommendations published by the International Committee of Medical Journal Editors (ICMJE). In summary, authorship should reflect significant contribution to the design and conduct of the trial, performance or interpretation of the analysis, and/or writing of the manuscript. All named authors must be able to defend the trial results and conclusions. MSD funding of a trial will be acknowledged in publications.

III. Participant Protection

A. Regulatory Authority and Ethics Committee Review (Institutional Review Board [IRB]/Independent Ethics Committee [IEC])

All protocols and protocol amendments will be submitted by MSD for regulatory authority acceptance/authorization before implementation of the trial or amendment, in compliance with local and/or national regulations.

The protocol, protocol amendment(s), informed consent form, investigator's brochure, and other relevant trial documents must be reviewed and approved by an IRB/IEC before being implemented at each site, in compliance with local and/or national regulations. Changes to the protocol that are required urgently to eliminate an immediate hazard and to protect participant safety may be enacted in anticipation of ethics committee approval. MSD will inform regulatory authorities of such new measures to protect participant safety, in compliance with local and/or national regulations.

B. Safety

The guiding principle in decision-making in clinical trials is that participant welfare is of primary importance. Potential participants will be informed of the risks and benefits of, as well as alternatives to, trial participation. At a minimum, trial designs will take into account the local standard of care.

All participation in MSD clinical trials is voluntary. Participants enter the trial only after informed consent is obtained. Participants may withdraw from an MSD trial at any time, without any influence on their access to, or receipt of, medical care that may otherwise be available to them.

C. Confidentiality

MSD is committed to safeguarding participant confidentiality, to the greatest extent possible, as well as all applicable data protection rights. Unless required by law, only the investigator, Sponsor (or individuals acting on behalf of MSD), ethics committee, and/or regulatory authorities will have access to confidential medical records that might identify the participant by name.

D. Genomic Research

Genomic research will only be conducted in accordance with a protocol and informed consent authorized by an ethics committee.

IV. Financial Considerations

A. Payments to Investigators

Clinical trials are time- and labor-intensive. It is MSD's policy to compensate investigators (or the sponsoring institution) in a fair manner for the work performed in support of MSD trials. MSD does not pay incentives to enroll participants in its trials. However, when enrollment is particularly challenging, additional payments may be made to compensate for the time spent in extra recruiting efforts.

MSD does not pay for participant referrals. However, MSD may compensate referring physicians for time spent on chart review and medical evaluation to identify potentially eligible participants.

B. Clinical Research Funding

Informed consent forms will disclose that the trial is sponsored by MSD, and that the investigator or sponsoring institution is being paid or provided a grant for performing the trial. However, the local ethics committee may wish to alter the wording of the disclosure statement to be consistent with financial practices at that institution. As noted above, all publications resulting from MSD trials will indicate MSD as a source of funding.

C. Funding for Travel and Other Requests

Funding of travel by investigators and support staff (e.g., to scientific meetings, investigator meetings, etc.) will be consistent with local guidelines and practices.

V. Investigator Commitment

Investigators will be expected to review MSD's Code of Conduct as an appendix to the trial protocol, and in signing the protocol, agree to support these ethical and scientific standards.

